Administration of vaccine ^j	X				
Serum sample for polio antibodies	X ^e			X	
Stool sample for viral culture/quantitative PCR, stool sample for potential poliovirus sequencing, stool sample for potential neurovirulence assay ^l	X-----X ^l		X	X ^l	X
Solicited systemic AEs (Diary) ^k	X-----X				
Remote contact for safety follow-up ^m					
Concomitant therapies ⁿ	X	X	X	X	X
Adverse events ⁿ	X	X	X	X	X
Reminder Code of Conduct ^o	X	X	X	X	X

- a. In case of early termination, the subjects will be asked to return to the clinical site within 14 days after discontinuation for assessments as outlined on Day 28.
- b. No study-related assessment is to be carried out before signing of the informed consent form.
- c. Including polio vaccination history.
- d. Includes weight and height at Day 0. After Day 0, symptom-directed physical examination.
- e. Prior to vaccination.
- f. Blood pressure and heart rate (supine) and oral body temperature. On Day 0, vital signs will be assessed prior to and 30 min after vaccination.
- g. For a list of assessments, please see Appendix 1: Overview of Laboratory assessments.

- h. In women of childbearing potential, a urine pregnancy test will be performed.
- i. Includes HBsAg, anti-HCV and anti-HIV antibodies, and IgA.
- j. The subjects will be kept under medical supervision for at least 30 min after vaccination.
- k. Solicited AEs will be collected for Days 0-7.
- l. Subjects will be asked to collect the first stool of every day in the provided container and to store this in the provided thermal bag with cooling elements: daily collection on Days 0 to 10 plus collection on Days 14, 21, V4 minus 1 or 2 days and V5 minus 1 or 2 days. At Day 0 the storage procedure will be explained and the collection material provided. Subjects who are still shedding virus in one of the 3 last stool samples will be asked to further collect 3 consecutive stool samples every 3 weeks till end of shedding.
- m. Remote contact (text message by sms, WhatsApp or email) on Day 3 and on Day 21 for safety follow-up and reminder stool collection scheme.
- n. Adverse events and intake of concomitant medication(s) will be monitored continuously from informed consent until the last study-related activity. The subjects can record unsolicited AEs on their diary card.

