- l. Subjects will be asked to collect the first stool of every day in the provided container and to store this in the provided thermal bag with cooling elements: after each vaccine dose, daily collection on Days 0 to 10 plus collection on Days 14, 21, V4 minus 1 or 2 days (= V7 minus 1 or 2 days after 2nd vaccination) and V8 minus 1 or 2 days. At Day 0, the storage procedure will be explained and the collection material provided. Subjects who are still shedding virus in one of the 3 last stool samples will be asked to further collect 3 consecutive stool samples every 3 weeks till end of shedding.
- m. Remote contact (text message by sms, WhatsApp or email) on Day 3 and on Days 21, 31 and 49 for safety follow-up and reminder stool collection scheme.
- n. Adverse events and intake of concomitant medication(s) will be monitored continuously from informed consent until the last study-related activity. The subjects can record unsolicited AEs on their diary card.
- o. After signing on screening visit, weekly reminder Code of Conduct by email or sms and on each visit to emphasize the need and importance of hygienic measures and respecting the inclusion/exclusion criteria until end of study.

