Comparative analyses to the Phase IV historical control arm will involve comparison of the binary shedding positivity endpoint using summary statistics, as well as 95% score-based confidence intervals for the difference in proportions at each time point.

The CCID₅₀ will be \log_{10} transformed, described with summary statistics, and compared to historical control using two-sided randomization tests and bootstrap 95% confidence intervals for the difference in median.

Time-to-shedding cessation will be summarized using quantiles and corresponding 95% confidence intervals, and tests between candidate vaccines and the historical control will be conducted with two-sided log-rank tests using a Type I error rate of 5%.

10.1.4 *Safety Data*

For an overview of primary and secondary endpoints, see Section 3.

Safety parameters will be tabulated and analyzed descriptively. Comparisons to the historical control will be based on descriptive statistics, using rates for adverse events and laboratory deviations, and continuous summaries for safety laboratory values.

Adverse Events

Analyses described below will be performed for solicited and unsolicited AEs as well as for SAEs, severe AEs.

The original terms used in the designated sections of the eCRFs by Investigators to identify AEs will be fully described and coded according to the current Medical

Dictionary for Regulatory Activities (MedDRA). For comparison with the M1 study M1 data will be recoded if necessary. All AEs will be summarized by type, seriousness, severity, causality, by group, and overall.

Separate tables and listings will be created for those subjects who died, discontinued the study vaccine due to an AE, or experienced a severe or serious AE. Summaries, listings, and narratives may be provided, as appropriate.

Clinical Laboratory Tests

Each continuous biochemistry and hematology laboratory test will be evaluated by means of descriptive statistics (i.e., number of subjects, mean, SD, median, minimum, and maximum) on the actual values, at each assessment time point and by group. Changes from baseline will also be summarized by assessment time point and by group.

Clinical laboratory test values will be evaluated according to Common Terminology Criteria for Adverse Events (CTCAE) version 4.03 (toxicity grades) or in accordance with the normal ranges of the clinical laboratory (below, within, or above normal range) for parameters for which no toxicity grades are defined.

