11.6 RECORDING OF ADVERSE EVENTS

All (S)AEs occurring during the clinical investigation must be documented in the source documents and on the AE forms of the eCRF. The Investigator will inquire about the occurrence of AEs/SAEs at every visit/contact during the study.

Whenever possible, diagnoses should be given when signs and symptoms are due to a common etiology (e.g., cough, runny nose, sneezing, sore throat, and head congestion should be reported as “upper respiratory infection”). Investigators must record their opinion concerning the relationship of the (S)AE to the study vaccine in the source documents and on the eCRF. All measures required for (S)AE management must be recorded in the source documents and reported according to Sponsor’s instructions.

All AEs occurring at any time during the study will be followed by the Investigator until satisfactory resolution (e.g., value back to baseline value) or stabilization or until last visit. If necessary, in order to obtain additional information to ensure safety to the subject, additional blood and urine samples may be taken at the discretion of the Investigator. Certain long-term AEs related to therapy cannot be followed until resolution within the setting of this study. In these cases follow-up will be the responsibility of the treating physician.

11.7 REPORTING OF SERIOUS ADVERSE EVENTS TO THE SPONSOR AND ASSIGN DATA MANAGEMENT AND BIOSTATISTICS GMBH

All SAEs independent of the circumstances or suspected cause must be reported on a Serious Adverse Event Form by the Investigator to the Sponsor and to Assign Safety Desk within 24 h of their knowledge of the event by fax ([contact]).

The SAE form should include a clearly written narrative describing signs, symptoms, and treatment of the event, diagnostic procedures, as well as any relevant laboratory data and any sequelae, in order to allow a complete medical assessment of the case and independent determination of the possible causality.

Follow-up and outcomes should be reported for all subjects who experience an SAE.

It is critical that the information provided on the Serious Adverse Event Form matches the information recorded in the source documents and on the eCRF for the same event.

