- b. No study-related assessment is to be carried out before signing of the informed consent form.
- c. Including polio vaccination history.
- d. Includes weight and height at Day 0. After Day 0, symptom-directed physical examination.
- e. Prior to vaccination.
- f. Blood pressure and heart rate (supine) and oral body temperature. On Day 0, vital signs will be assessed prior to and 30 min after vaccination.
- g. For a list of assessments, please see Appendix 1: Overview of Laboratory assessments.
- h. In women of childbearing potential, a urine pregnancy test will be performed.
- i. Includes HBsAg, anti-HCV, and HIV antibodies.
- j. The subjects will be kept under medical supervision for at least 30 min after vaccination.
- k. Solicited AEs will be collected for Days 0-7.
- l. Subjects will be asked to collect the first stool of every day in the provided recipient and bring the samples with them at the next scheduled visit. Daily collection on Days 0 to 10 plus collection on Days 14, 21 and V4 minus 1 or 2 days. Stool samples need to be stored by the subject at 4-8°C for maximum 7 days, before brought to the vaccine center. At Day 0 the storage procedure will be explained and the collection material provided.
- m. Daily remote contact (text message by sms, WhatsApp or email) from Day 0 to Day 10 and also on Day 21 and 42.

- n. Adverse events and intake of concomitant medication(s) will be monitored continuously from informed consent until the last study-related activity. The subjects can record unsolicited AEs on their diary card.

TIME AND EVENTS SCHEDULE – GROUP 2

Assessments	Group 2							Follow-up contact
	1	2	3	4	5	6	7	
Time of Visit (days)	D 0	D 7 (+/- 2D)	D 14 (+/- 3D)	D 28 (+/- 2D)	D 35 (+/- 2D)	D 42 (+/- 3D)	D 56 ^a (+/- 2D)	D 70 (+/- 4D)
Visit Window								
Informed consent ^b	X							
In-/exclusion criteria	X							
Medical history/concomitant diseases	X							
Medication history ^c	X							
Demographic data	X							
Physical examination ^d	X ^e	X		X ^e	X			X
Vital signs ^f	X ^{e,f}	X		X ^e	X			X
Clinical laboratory tests ^g	X ^e	X		X ^e	X			X
Pregnancy test ^h	X			X ^e				
Serology ⁱ	X							
Randomization	X							
Administration of vaccine ^j	X			X				
Serum sample for polio antibodies	X ^e			X ^e				X
Stool sample for viral culture/quantitative PCR ^l , stool sample for potential poliovirus sequencing, stool sample for potential neurovirulence assay	X----- X ^l	X	X----- X ^l		X			
Solicited systemic AEs (Diary) ^k	X----- X		X----- X					

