Remote contact for safety follow-up ^m	X-----X ^m		X-----X ^m					X
Concomitant therapies ⁿ	X	X	X	X	X	X	X	X
Adverse events ⁿ	X	X	X	X	X	X	X	X

- a. In case of early termination the subjects will be asked to return to the clinical site within 14 days after discontinuation for assessments as outlined on Day 56.
- b. No study-related assessment is to be carried out before signing of the informed consent form.
- c. Including polio vaccination history.
- d. Includes weight and height at Day 0. After Day 0, symptom-directed physical examination.
- e. Prior to vaccination.
- f. Blood pressure and heart rate (supine) and oral body temperature. On Day 0 and Day 28 (Group 2 only), vital signs will be assessed prior to and 30 min after vaccination.
- g. For a list of assessments, please see Appendix 1: Overview of Laboratory assessments.
- h. In women of childbearing potential, a urine pregnancy test will be performed.
- i. Includes HBsAg, anti-HCV, and HIV antibodies.
- j. The subjects will be kept under medical supervision for at least 30 min after vaccination.
- k. Solicited AEs will be collected for Days 0-7 and Days 28-35.

- p. Subjects will be asked to collect the first stool of every day in the provided recipient and bring the samples with them at the next scheduled visit. After each vaccine dose, daily collection on Days 0 to 10 plus collection on Days 14, 21 and V4 minus 1 or 2 days (=V7 minus 1 or 2 days after 2nd vaccination). Stool samples need to be stored by the subject at 4-8°C for maximum 7 days), before brought to the vaccine center. At Day 0 the storage procedure will be explained and the collection material provided.
- q. Daily remote contact (text message by sms, WhatsApp or email) from Day 0 to Day 10 and also on Day 21 after the first vaccine dose. Thereafter, daily remote contact from Day 28 to Day 38 and also on Day 49 and Day 70.
- r. Adverse events and intake of concomitant medication(s) will be monitored continuously from informed consent until the last study-related activity. The subjects can record unsolicited AEs on their diary card.

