6.5.1 Primary Safety Endpoints

- Solicited adverse events:
 - Serious/severe solicited adverse events will be summarized by group, by post-vaccination time period as well as overall (under maximum severity), and by term by post-vaccination time period as well as overall (under maximum severity), as well as listed.
- Unsolicited adverse events:
 - Serious/severe unsolicited AEs will be summarized by group, maximum causality and by class (serious vs severe) under maximum causality, by post-vaccination

time period (prior to dose 2 vs following dose 2) as well as overall, and reasons for SAE classification (wherever such subcategories are relevant), as well as by SOC and PT among serious events only (and among those serious and related), and among severe events only (and among those severe and related). These events will also be listed.

- Listings will be prepared for those subjects who died or withdrew from the study due to an AE.

Two-sided p-values from the Fisher exact test of the number of subjects with an event will be presented for:

- Severe solicited events (overall, and by event term)
- Any serious unsolicited event
- Any serious and related unsolicited event
- Any severe unsolicited event
- Any severe and related unsolicited event

These comparisons will be conducted for the following groups:

- UAM4 Groups 1 & 2 vs UAM1 Groups 1 & 2
 - Post-dose-1 and overall, TVP
- UAM4 Group 2 vs UAM1 Group 2
 - Post-dose-2, TVP subjects who received both doses
- UAM4 Groups 3 & 4 vs UAM1 Groups 1 & 2
 - Post-dose-1 and overall, TVP
- UAM4 Group 4 vs UAM1 Group 2
 - Post-dose-2, TVP subjects who received both doses
- UAM4 Group 5 vs UAM4 Group 7
 - Post-dose-1, post-dose-2, and overall, TVP
- UAM4 Group 6 vs UAM4 Group 7
 - Post-dose-1, post-dose-2, and overall, TVP

Comparisons for both solicited and unsolicited events will be conducted separately for post-dose-1 and post-dose 2, as well as following any dose. Comparisons involving post-dose-2 data will include only subjects receiving both doses.

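### Unsolicited adverse events are compared with UAM1 as if they were sought equally in both studies, but ascertainment differs in both directions and the SAP does not allow for it

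*SAP*

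**What the plan says.** **The comparison.** SAP 6.5.1 states that "Two-sided p-values from the Fisher exact test of the number of subjects with an event will be presented for" severe solicited events, and for serious, serious and related, severe, and severe and related unsolicited events. Groups 1 and 2 combined, Groups 3 and 4 combined, Group 2 and Group 4 are each tested against the matching UAM1 groups. SAP 6.5.2 summarises unsolicited AEs of every severity, and SAP 5.1 places UAM1 summaries alongside those of OPV-vaccinated subjects. Clinical and laboratory AEs are not separated. Protocol 10.1.4 had planned something lighter: "Comparisons to the historical control will be based on descriptive statistics, using rates for adverse events and laboratory deviations". SAP section 7 does not list the change.

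**Contact after dosing.** For UAM1, Protocol Appendix 3 gives "Daily remote contact (text message by sms, WhatsApp or email) from Day 0 to Day 10 and also on Day 21 and 42" in Group 1 and, for the second dose in Group 2, "Thereafter, daily remote contact from Day 28 to Day 38 and also on Day 49 and Day 70". For UAM4, Protocol 8.1 gives "Remote contact (text message by sms, WhatsApp or email) on Day 3 and on Day 21 for safety follow-up and reminder stool collection scheme" in Groups 1 and 3, and "on Day 3 and on Days 21, 31 and 49 for safety follow-up and reminder stool collection scheme" in the two-dose groups. Protocol 11.6 links contact to AE enquiry: "The Investigator will inquire about the occurrence of AEs/SAEs at every visit/contact during the study".

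**Laboratory and examination.** UAM1 has safety laboratory tests on Days 0, 7 and 28 (and 35 and 56 in Group 2). UAM4 has Days 0, 7, 14 and 28 (and 35, 42 and 56 in Groups 2 and 4), with physical examination and vital signs at the added visits. Protocol 11.2 makes any laboratory value above grade 1 an AE automatically.

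**Alignment.** SAP 5.1 aligns CRF terms and the coding dictionary between the studies. It does not deal with how often events were sought.

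**The concern.** A historical comparison of AE rates can be read directly only if events had a similar chance of being recorded in both studies. Here they did not. Fewer enquiries in the days after dosing can leave minor clinical events unrecorded in the candidate arms. A true excess over Sabin then shrinks, and an equal or lower rate may be taken as reassurance. More laboratory draws, with an automatic rule for recording AEs, act the other way and can make a candidate look worse.

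Safety relative to Sabin in OPV-vaccinated adults is a primary objective. A p-value that mixes two ascertainment differences of unknown size cannot be read as evidence for or against a difference in safety.

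**Working it through.** **1. The plan's own figure.** The only safety sizing for the OPV groups (Protocol 10.2) is 45 subjects for a 90% chance of at least one event at a 5% rate: 1 − 0.95^45 = 0.901, and 45/0.90 = 50. It reproduces. No power is stated for the Fisher tests against UAM1.

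**2. Scheduled ascertainment,** counted from Protocol 8.1 and Appendix 3:

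| | UAM1 | UAM4 |
|---|---|---|
| Remote contacts, Days 0-10 after a dose | 11 | 1 |
| Remote contacts, one dose / two doses | 13 / 25 | 2 / 4 |
| Distinct contact or visit days, one / two doses | 15 / 28 | 7 / 12 |
| In-person visits, one / two doses | 4 / 7 | 5 / 8 |
| Post-baseline laboratory draws, one / two doses | 2 / 4 | 3 / 6 |

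The distinct days for one dose are 0-10, 14, 21, 28 and 42 in UAM1, and 0, 3, 7, 14, 21, 28 and 42 in UAM4. Remote contact favours detection in UAM1; visits and laboratory draws favour detection in UAM4. From Day 11 to Day 28 after a dose, contact days coincide (14, 21, 28; after dose 2: 42, 49, 56), but UAM4 adds examination and vital signs at the first of these.

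**3. Which events are exposed.** Severe solicited events come from the same Day 0-7 diary in both studies, so at most the prompting differs. SAEs, and AEs that prevent normal activity, are the least likely to be missed when a subject is seen on Day 7 and Day 14. Mild and moderate clinical AEs, summarised in 6.5.2 without a test, are the most exposed.

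**4. Size for the 6.5.2 summaries (assumed values).** Let p be the true rate of any unsolicited AE, s the share of affected subjects with early onset only, and d the share of those captured in UAM4 relative to UAM1. The apparent lowering is p × s × (1 − d). Uniform onset with one event per subject gives s = 11/43 = 0.26 on the one-dose schedule; s is smaller if subjects have several events and larger if events cluster after dosing. With p = 40%:
- s = 0.26: 0.40 × 0.26 × 0.1 = 1.0 point (d = 0.9), to 0.40 × 0.26 × 0.3 = 3.1 points (d = 0.7).
- s = 0.50: 2.0 points (d = 0.9) to 6.0 points (d = 0.7).

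**5. Size for a tested class (assumed values).** Let c be the share of clinical events captured in UAM4 relative to UAM1, and l the share of subjects with a severe laboratory AE found only through UAM4's extra ascertainment. The observed candidate rate is 1 − (1 − pc)(1 − l). Exact two-sided 5% Fisher test, 100 v 100:

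| True rates (candidate v UAM1) | c | l | Observed candidate rate | Flags candidate higher | Flags candidate lower |
|---|---|---|---|---|---|
| 20% v 10% | 1.0 | 0 | 20.0% | 44% | 0% |
| 20% v 10% | 0.9 | 0 | 18.0% | 31% | 0% |
| 20% v 10% | 0.8 | 0 | 16.0% | 19% | 0% |
| 10% v 10% | 1.0 | 0 | 10.0% | 1.4% | 1.4% |
| 10% v 10% | 0.8 | 0 | 8.0% | 0.4% | 4.3% |
| 10% v 10% | 0.8 | 5% | 12.6% | 5.5% | 0.3% |
| 10% v 10% | 0.8 | 10% | 17.2% | 26% | 0% |

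The two effects cancel at l = p(1 − c)/(1 − pc). At p = 10% and c = 0.8 this is 0.02/0.92 = 2.2%. Across p = 5-20% and c = 0.9-0.7 it runs from 0.5% to 7.0%. For severe events c should lie near 1, so a smaller l suffices.

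**The case against.** The strongest case on the other side has four parts.

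- **A missing contact day is not a missed event.** The Day 3, 7 and 14 contacts can pick up the preceding days, AEs are monitored continuously, and the same sentence stands in both schedules: "The subjects can record unsolicited AEs on their diary card". This holds. It softens the gap without equalising prompting, and it means that any capture value below 1 is an assumption.
- **The enquiry rule is UAM4's.** UAM1 is available only as a synopsis and schedules. Its contact row is labelled as safety follow-up, but the content of the daily messages is not given. UAM4 also sends weekly Code of Conduct reminders, which are not in the counts above. This stands as a limit on the size of the effect.
- **The tested classes are the least affected.** No Fisher test of any unsolicited AE is planned, so a large loss of power for that endpoint would describe a test that the SAP does not contain. This stands.
- **The p-values carry no decision rule.** Protocol 10.1 leaves the UAM1 comparisons to the SAP, and exact intervals for proportions and a listing with onset day are already planned. This lowers the stakes, but neither addresses unequal ascertainment.

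A reader might infer that the UAM1 Fisher tests as a whole are tilted towards making the candidates look as safe as Sabin or safer. The documents do not support that. The severe unsolicited class includes laboratory AEs, which UAM4 seeks harder, and Protocol 1.3.1 reports that severe unsolicited AEs in the first-in-human study were mostly transient laboratory abnormalities. The tilt could run against the candidates.

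**Conclusion.** The point holds as a two-way difference in ascertainment that the SAP neither adjusts for nor mentions. For clinical unsolicited AEs in the first 10 days after a dose, the contact schedule can favour the candidates, by roughly 1 to 6 percentage points at an assumed 40% rate; little effect is expected on severe AEs, SAEs or diary-solicited events. For the severe unsolicited class as tested, the extra UAM4 draws and examinations and the automatic AE rule can push the other way, and the net direction cannot be determined.

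All sizes rest on assumed event rates, capture shares and laboratory detection; the documents give none of these. UAM1's laboratory panel and its rule for recording laboratory values as AEs are also not in the synopsis, so the laboratory effect cannot be bounded. The randomised comparisons of Groups 5 and 6 with Group 7 share one schedule and are not affected. The primary immunogenicity analysis is untouched.

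**What to change.** For the UAM1 contrasts of unsolicited AEs in SAP 6.5.1 and 6.5.2:

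1. Report clinical and laboratory AEs separately, with laboratory AEs limited to draw days and parameters common to both studies.
2. Add a sensitivity table of clinical AEs by onset: Days 0-10 after a dose, Days 11-28 after a dose, and after Day 28 following the last dose. Give risk differences with 95% Miettinen-Nurminen intervals. Note that Days 11-28 have equal contact days but an extra UAM4 examination and vital signs at Day 14 after each dose (study Day 42 after dose 2), so this window is not fully like-for-like.
3. Present these contrasts as descriptive, in line with Protocol 10.1.4, in place of the Fisher p-values against UAM1. Alternatively keep those p-values, label them descriptive and list them in SAP section 7.
4. State the contact difference, and state that an equal or lower Day 0-10 clinical unsolicited rate in UAM4 is not on its own evidence of similar or better safety.

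Keep the full-period summaries and the Fisher tests of Groups 5 and 6 against Group 7.

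The cost is SAP wording and a few tables from onset dates already collected, with no new data or subjects. The downside is small counts and wide intervals in each window, so the table supplements the full-period summary and does not replace it.
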